## **5.11 Maternal and Infant TB**

Validation: The analysis programs in this section will be validated, but not double-programmed.

Note: Mother-infant pairs will be excluded if the mother had TB diagnosis at study entry.

- Listing of active TB events, including blinded ID, treatment arm, event week, site diagnosis, SERC decision, event grade and INH resistance testing results (if available), shown separately for mothers and infants
- Table of SERC-assessed TB and death endpoints: number (%) by arm of the following:
  - Maternal TB cases by type (PULMONARY: 220021-CONFIRMED, 220022-PROBABLE; EXTRAPULMONARY: 220031-CONFIRMED, 220032-PROBABLE)
  - Infant TB cases by type (PULMONARY: 220021-CONFIRMED, 220022-PROBABLE, POSSIBLE; EXTRAPULMONARY: 220031-CONFIRMED, 220032-PROBABLE; CONGENITAL TB).
  - Death of infant
  - Death of mother
  - Maternal TB or maternal death
  - Infant TB or infant death
  - Maternal TB, maternal death, infant TB, or infant death

As event numbers warrant:

- Table of intent-to-treat analysis of difference in endpoint rates between arms, based on stratified Mantel-Haenszel estimates at week 48 postpartum (primary) and simple proportions (sensitivity), stratified by gestational age, for the following endpoints:
  - Maternal TB
  - Infant TB
  - Death of infant
  - Death of mother
  - Maternal TB or maternal death
  - Infant TB or infant death
  - Maternal TB, maternal death, infant TB, or infant death
- Kaplan-Meier plot of time to endpoint from randomization date by study arm and by gestational age, with number of events and number at risk for the following endpoints:
  - Maternal TB
  - Infant TB
  - Death of infant

- Death of mother
- Maternal TB or maternal death
- Infant TB or infant death
- Maternal TB, maternal death, infant TB, or infant death

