### **2.2 Secondary Objectives**

1. To compare safety and toxicity of INH *in utero* exposure and on infants on study
2. To compare TB incidence and all-cause mortality in HIV-infected women and their infants enrolled on study
3. To compare overall safety and hepatotoxicity, as well as evaluate risk factors for these outcomes, during pregnancy and immediate postpartum in women on immediate versus deferred INH therapy
4. To evaluate for INH resistance among *M.tb.* isolates from HIV-infected women and infants who develop TB while on study
5. To evaluate the intensive pharmacokinetics of INH and selected ARV drugs in a subset of HIV-infected pregnant and postpartum women receiving HAART
6. To evaluate and compare the performance characteristics of IGRA (TB ELISPOT and QGIT) with TST in HIV-infected women and their infants
7. To compare adherence in women initiating immediate versus deferred INH preventive therapy via self-report and pill counts

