#### 4.2 Analysis of Secondary Objectives

Maternal TB, maternal death, infant TB and infant death will be analyzed separately and as combined events. Efficacy of INH will be assessed primarily by comparing event rates between women in the immediate and deferred arms by 48 weeks postpartum.

A 95% confidence interval for the absolute difference in event rates will be computed using study entry gestational age-stratified Mantel-Haenszel estimates. Unweighted (i.e., ignoring stratification) estimates for the difference in rates will also be reported.

Strategies for censoring will vary depending on the efficacy outcome of interest. For analyses of maternal TB, any maternal death not caused by TB will not be considered an event and any maternal death of unknown cause will be considered an event. Similarly, for analyses of infant TB, any infant death not caused by TB will not be considered an event and any infant death of unknown cause will be considered an event. Sensitivity analysis to assess the effect of this strategy includes coding death due to unknown cause as a non-event.

This will be a modified intent-to-treat analysis, with participants analyzed according to randomized study arm, excluding those who were determined to have active TB at entry.

For final analyses, supplementary analyses will include estimation of differences in these individual/combined endpoint rates between the two arms based on simple estimates for proportions.

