## **5.7 Maternal Mortality**

Validation: The analysis programs in this section will be validated, but not double-programmed.

- Listing of maternal deaths including public ID, treatment arm, weeks on study, stage of pregnancy, site assessment of primary COD and treatment attribution, and IERC treatment attribution [STATUS, PE1414, TRAC]
- Listing of maternal deaths including the following peak lab values: ALT, AST, total bilirubin, alkaline phosphatase, GGT, INR, total protein, and albumin [PE6812, PE6817]

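### The entry-TB exclusion is applied to deaths as well as to TB incidence, and 5.11 widens it from the participant to the mother-infant pair

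*SAP*

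**What the plan says.** Secondary objective 2 (SAP 2.2) is "To compare TB incidence and all-cause mortality in HIV-infected women and their infants enrolled on study". Secondary objective 4 concerns INH resistance in "isolates from HIV-infected women and infants who develop TB while on study".

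Section 4.2 sets out the endpoints: "Maternal TB, maternal death, infant TB and infant death will be analyzed separately and as combined events". It names the analysis set as modified intent-to-treat, "excluding those who were determined to have active TB at entry".

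Section 5.11 opens with the note "Mother-infant pairs will be excluded if the mother had TB diagnosis at study entry". Under it stand the listing of active TB events, the table of TB and death endpoints, the Mantel-Haenszel rate differences and the Kaplan-Meier plots. The last three include death of mother, death of infant and the composites. The rate-difference output is headed "Table of intent-to-treat analysis of difference in endpoint rates between arms". The TB listing carries "event grade and INH resistance testing results (if available), shown separately for mothers and infants", and no other component of the report presents resistance results.

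**The concern.** Excluding women who already have TB is sound when the question is who acquires TB. It has no such justification for death from any cause. Every randomized woman is at risk of death from randomization and every live-born infant from birth, so dropping some of them gives up part of the randomized comparison without making the endpoint clearer.

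The pair-level wording has a second effect. An infant is removed because of the mother's status, not its own. Infants of mothers with TB at entry are a natural group in which to look for congenital TB, which section 3.2 names as part of the infant TB endpoint.

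At stake are a mortality result that does not match its objective, infant TB events that are not counted, and two statements of one exclusion rule from which programmers could build different analysis sets.

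**Working it through.** The SAP states no figure on this point, so there is none to reproduce. The check is mainly a comparison of text, followed by a short illustration of size.

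**1. The exclusion rule as stated in two places**

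| Feature | Section 4.2 | Section 5.11 |
|---|---|---|
| Label | modified intent-to-treat | intent-to-treat (rate-difference table) |
| Unit removed | the participant with TB at entry | the mother-infant pair |
| Criterion | active TB at entry, as determined | TB diagnosis at entry |
| Endpoints affected | TB and death, single and combined | every output in the section |

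The criteria can select different women. Section 1.2 makes women with suspected TB ineligible, so a set defined by a diagnosis already made at entry should be close to empty. A set defined by a determination of TB at entry can also include disease recognised later.

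**2. Maternal deaths elsewhere in the report**

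- Section 5.7 is a "Listing of maternal deaths including public ID, treatment arm, weeks on study, stage of pregnancy". It carries no exclusion, but it estimates no difference between arms.
- Sections 4.1.1 and 5.9 code all deaths as events in a sensitivity analysis of the primary endpoint. That analysis mixes deaths with drug-related adverse events and is not a mortality comparison.
- No other output compares maternal deaths between arms. The comparison in 5.11, itself produced only if event numbers warrant it, is therefore the only one, and it carries the exclusion.

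**3. Infant deaths elsewhere**

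The infant safety table in section 5.10 counts infant and neonatal deaths. Outputs are by arm (section 5, opening notes), and 5.10 compares outcomes with exact tests. No entry-TB exclusion applies there. Infant deaths are therefore compared in all infants, but 5.11 would show a second comparison in a different population, and neither is named as the leading one.

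**4. Infant TB and resistance**

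Objective 4 and the resistance outcomes in section 3.2 cover infants who develop TB on study and set no condition on the mother's status. The listing in 5.11 is the only resistance output, and the pair rule removes these infants from it.

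**5. Size (illustration)**

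Inputs: target enrolment of 950 with equal allocation (section 1.2), so 950 / 2 = 475 per arm. Death rates and the number of excluded deaths are assumptions, because the SAP gives neither. Simple proportions are used.

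- Shift per excluded death in one arm: 1 / 475 = 0.21 percentage points.
- Five excluded deaths in one arm: 5 / 475 = 1.05 points. Allowing for the smaller denominator after exclusion, the shift is about 1.0 point.
- One excluded pair with no death: less than 0.01 points.
- 95% confidence interval half-width for the difference, 1.96 × sqrt(2p(1 − p) / 475):

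| Assumed death rate p | Half-width (percentage points) |
|---|---|
| 1% | 1.27 |
| 2% | 1.78 |
| 4% | 2.49 |

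One excluded death is small against these widths. Several in one arm would not be.

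**The case against.** The best defence is that the exclusion is prespecified. Section 4.2 frames these endpoints as efficacy of INH, and removing people who already have the outcome disease from a prevention analysis is conventional. Using one population for single and composite endpoints also keeps the tables consistent. That defence stands for TB incidence. For death it explains the choice, but it does not make the result answer objective 2, and it does not account for the intent-to-treat label or the widening to pairs in 5.11.

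It is also fair to say that the deaths are not hidden: infant deaths are compared in 5.10 and maternal deaths are listed by arm in 5.7. That stands, and it limits the mortality point mainly to the maternal comparison.

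A reader might infer more than the documents support:

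- **That mothers' resistance results are wrongly lost.** Objective 4 concerns TB that develops on study. TB already present at entry did not, so leaving out that mother's isolate agrees with the objective. The point holds only for infants.
- **That the exclusion makes immediate INH look safer.** It applies to both arms, and nothing in the SAP shows which arm would lose more deaths.
- **That entry-TB status is assigned unblinded.** The trial is double-blind, and the SAP refers the review process to a separate Endpoint Review Process document. Silence here shows nothing.
- **That a sizeable share of maternal deaths is removed.** Such a share needs the prevalence of TB at entry, its fatality and the total number of deaths. The SAP gives none of them.

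**Conclusion.** The point holds in a limited form. Followed as written, the plan gives a maternal mortality comparison that omits randomized women with TB at entry, contrary to objective 2 and to the label in 5.11. It also drops on-study TB, including congenital TB, in their infants from the infant TB endpoint and from the resistance listing. Sections 4.2 and 5.11 disagree on label, unit and criterion.

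The numerical effect is probably low, because entry screening should leave few such pairs. It is about 0.2 percentage points per excluded death in one arm, given 475 per arm, against a half-width of about 1.3 to 2.5 points at assumed death rates of 1% to 4%. The number of affected pairs is not in the document, so the actual effect cannot be stated. The change is worth making because it is specific and inexpensive.

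**What to change.** 1. Limit the entry-TB exclusion to the TB incidence endpoints.
2. Analyse death of mother and death of infant in all randomized women and their live-born infants. At minimum, prespecify this as a sensitivity analysis beside the modified intent-to-treat result.
3. Show the composite endpoints both with and without the exclusion.
4. Keep infants of mothers with TB at entry in the TB and resistance listing, with a flag.
5. Use one label, one unit of exclusion and one criterion for TB at entry in sections 4.2 and 5.11.

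Cost: SAP wording and a population flag in existing programs. No new data are needed.

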## **5.12 Changes in ARV regimen**

Validation: The analysis programs in this section will be validated, but not double-programmed.

- Table of ARV discontinuation: number (%) discontinuing at least one component of baseline ARV regimen by category (EFV-based regimen vs. non-EFV ARV regimen) [PE0421]
- Table of changes in Efv use: number (%) with the following changes in Efv use, by phase of pregnancy (entry to < delivery, delivery to < week 12 PP, week 12 PP to week 48 PP) [STATUS, PE0421]:
  - Switched from an Efv-containing regimen at entry to a non Efv-containing regimen
  - Switched from a non Efv-containing regimen at entry to an Efv-containing regimen

## **5.13 Vital Status of Participants Lost to Follow-up**

Validation: The analysis programs in this section will be validated, but not double-programmed.

- Table of number (%) of participants lost to follow-up with vital status data and source of information by category (participant, family member, neighbor, medical records, other) [VSW0024]
- Table of number (%) of mothers who experienced the following since last seen on study [VSW0024]:
  - Death
  - Hospitalization
  - TB diagnosis
  - Delivery by pregnancy outcome
- Table of number (%) of infants who experienced the following since last seen on study [VSW0024]:
  - Death
  - Hospitalization
  - TB diagnosis

## **5.14 Report Appendices**

- Listing by arm of enrolled women who experienced primary safety endpoint, including: blinded ID; adverse event and grade associated with safety endpoint; week of event;

whether treatment was temporarily discontinued, permanently discontinued, or not; week of treatment discontinuation [STATUS, PE4005, TRAC]
